12.4. Unsolicited Adverse Events

Any AEs reported by maternal subjects will be categorized as unsolicited events and Medical Dictionary for Regulatory Activities (MedDRA) coded by system organ class (SOC) and preferred term (PT). Solicited events with an onset after the solicitation period will also be classified as unsolicited AEs. Unsolicited events that occur within 7 days following vaccination should also be recorded in the subject diary. If any grade 3 unsolicited event is reported during this period, maternal subjects should be encouraged to contact the investigator by telephone. The investigator may request an *ad hoc* clinic visit at his/her judgment, and should enter any grade 3 unsolicited adverse event reported by telephone in the unsolicited AE eCRF promptly, even if the balance of diary data is not yet available. Continuing non-serious solicited AEs lasting beyond the 7-day diary period reported on the AE CRF to collect the symptom end date will not be summarized in the unsolicited AE tables. Solicited AEs reported on the AE CRF will be treated as solicited AEs and will be summarized in solicited AE tables only.

Any AEs reported in infants will be categorized as unsolicited events and MedDRA coded by SOC and PT. These can include, but are not limited to, abnormalities in vital signs, metabolic screening and developmental tests, neonatal hearing, congenital anomalies, respiratory failure, perinatal infections, neonatal death, complications that result in extended hospitalization; as well as any other SAE (as defined in Section 8.5 of the Protocol) or MAE or SNMC (as defined in Section 8.4 of the Protocol).

All unsolicited AEs will be assessed for severity and for causality for infants and maternal subjects.

The following summaries of unsolicited AEs will be presented for all maternal subjects in the Safety Population as part of the secondary analysis of safety:

- Overall summary of unsolicited AEs by treatment group (Day 0 post-vaccination to Day of delivery -1 and also Day 0 post-vaccination to Delivery +180).
- A summary by severity (mild, moderate, or severe), MedDRA SOC, PT, and treatment group (Day 0 post-vaccination to D+180).
- A summary by relationship to study vaccine, MedDRA SOC, PT, and treatment group (Day 0 post-vaccination to D+180).
- A summary of severe and related AEs, MedDRA SOC, PT, and treatment group (Day 0 post-vaccination to D+180).

For infants, the following summaries of unsolicited AEs will be presented:

- An overall summary of unsolicited AEs (Delivery to Delivery + 180 days and/or Delivery + 364 days).
- A summary by severity (normal, mild, moderate, or severe), MedDRA SOC, PT, and treatment group (Delivery to Delivery + 180 days and/or Delivery + 364 days).
- A summary by relationship to study vaccine, MedDRA SOC, PT, and treatment group (Delivery to Delivery + 180 days and/or Delivery + 364 days).
- A summary of severe and related AEs, SAEs, MAEs, and SNMCs, by MedDRA SOC, PT, and treatment group (Delivery to Delivery + 180 days and/or Delivery + 364 days).

12.5. Medically-Attended Events and Significant New Medical Conditions

These classes of events will be collected at all study visits, and if offered spontaneously by the subject at any time.

MAEs are adverse events which result in an unscheduled visit to a healthcare provider due to symptomatic illness or injury. These may include office visits, clinic visits, home consultations, or emergency room evaluations for non-life-threatening events that do not result in hospitalization (life-threatening events or hospitalizations are SAEs, see Section 8.5 of the Protocol).

SNMCs are adverse events that are new (that is, not present at baseline), clinically significant (meaning that they imply an important change in the subject's long-term health status), and typically chronic (requiring an ongoing change in the subject's medical management). This category is not meant to include minor or transient diagnoses or age-related changes.

MAEs and SNMCs will be recorded and summarized from Day 0 to Delivery + 180 days for the maternal subjects and from Delivery to Delivery + 180 days for the infants for the unblinded analysis; and from Delivery to Delivery + 364 following study completion for the final analysis, for all infants in the Safety Population. Note that MAEs and SNMCs are also included in the overall summary of AEs.

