8.4 Medically-Attended Events and Significant New Medical Conditions

Medically-attended events (MAEs) are adverse events which result in an unscheduled visit to a healthcare provider (e.g., physician, midwife, or other provider as per local standards of care) due to symptomatic illness or injury. These may include office visits, clinic visits, home consultations, emergency room evaluations for non-life-threatening events, and hospitalizations.

Significant new medical conditions (SNMCs) are adverse events that are new (that is, not present at baseline), clinically significant (meaning that they imply an important change in the subject’s long-term health status), and typically chronic (requiring an ongoing change in the subject’s medical management). This category is not meant to include minor or transient diagnoses or age-related changes. For example, while new diagnoses of presbyopia or tinea versicolor are chronic conditions, they are not SNMCs because no significant change in health status is implied. Similarly, adverse events which are isolated, treatable events that resolve and do not require chronic therapy are also not SNMCs (examples could include an uncomplicated acute urinary tract infection or a simple fracture resolved with conservative treatment and with no residual disability). In contrast, new diagnoses of rheumatoid arthritis or coronary artery disease are SNMCs because they imply a long-term change in health status and require ongoing medical management.

The eCRF/eSource will provide a field in which the investigator may designate AEs as MAEs, SNMCs, or both. Because of the significance of the designation for the subject’s health, long-term medical management, and for evaluation of vaccine safety, SNMCs are expected to be substantiated diagnoses, not isolated symptoms which might or might not be an SNMC, and the Investigator should record sufficient data in the source document to support the diagnosis.

Full details of MAEs and SNMCs (i.e., nature, date of onset and recovery (if applicable) as well as an assessment of severity, relationship to study agent, seriousness, treatment, and outcome) will be recorded in the source documentation and captured in the eCRF or entered into the eSource directly, and will require the Investigator(s) causality assessment.

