Synopsis (Infant Subject Study D+180 Visit and Safety Endpoints, Time and Events Table); Sections 3.3.4.1, 6.1.3.7, 6.1.3.9, and 8.3.1, Appendix 1	
A new section for the “Ages & Stages Questionnaires®, Third Edition (ASQ-3™)” was created. Parents/guardians of infant subjects with a positive screen detected at both 6 and 12 months of age (as this is an AE), or first appearing at 12 months of age, will be offered repeat Ages and Stages Questionnaire (ASQ)-3 screening at 15 and 18 months of age in a follow-on study. In addition, appropriate referrals for diagnostic pediatric developmental testing (according to local standards of care) will also be advised for these infants.
 
The ASQ-3 screening will be performed on all infant subjects.

Synopsis (RSV Surveillance); Section 6.2	
Content was reorganized and clarified to harmonize with operational activities and to be consistent with supplemental study documents (e.g., Study Identification Card, electronic case report forms). A “Definitions and Rules for RSV Surveillance” section was also added.
 
Clarified that maternal and infant subjects with ongoing respiratory episodes at the D+180 visit will be followed weekly until symptoms have resolved or have returned to baseline.

Section 8.2.3	The toxicity grades used to assess for severity of clinical laboratory parameters will be based on third-trimester values published in Sheffield et al. [2013]. Normal ranges for these parameters will also be based on reference ranges appropriate for women in the third trimester of a pregnancy as described in Sheffield et al.
Sections 8.2.4 and 8.8.1	A toxicity grading scale to assess for severity of an abnormal fetal heart tone value was developed and provided in Table 7.

Location of Change	Change/Modification in Version 4.0
Section 8.4	In addition to being serious adverse events, hospitalizations will now be categorized as medically-attended events.
Section 8.6, Table 5	The term “Intrauterine Growth Restriction or Retardation (IUGR)” will now be captured as a separate entity, distinct from “Small for Gestation Age (SGA)” as a Maternal/Fetal/Neonatal Adverse Event of Special Interest.
Section 8.7	The procedure for SAE reporting was revised to be compliant with Novavax internal standard operating procedures.

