4.3.2. In Maternal Subjects

- Percentages of subjects with solicited injection site and systemic reactogenicity within seven days of vaccination.
- Percentages of subjects with unsolicited (local and systemic) adverse events (AEs), unscheduled medically-attended adverse events (MAEs), significant new medical conditions (SNMCs), and serious adverse events (SAEs) through delivery and six (6) months thereafter.
- Clinical safety laboratory assessments of select serum chemistry and hematology parameters through delivery.

- Percentages of subjects with Caesarean, vaginal, or instrument-assisted vaginal modes of delivery.
- Percentages of subjects with post-immunization onset of specific complications of third-trimester pregnancy and delivery including (but not necessarily limited to):
 - Pregnancy complications:
 - Stillbirth,
 - Preterm birth (moderate to late preterm: 32 to < 37 weeks of gestation; very preterm: 28 to < 32 weeks of gestation),
 - Preterm premature rupture of membranes,
 - Placental abruption,
 - Hypertensive disorders of pregnancy including: gestational hypertension, pre-eclampsia/eclampsia,
 - Third-trimester hemorrhage, and
 - Gestational diabetes.
 - Labor and delivery complications:
 - Emergency Caesarean (C)-section for maternal or fetal indications,
 - Postpartum hemorrhage,
 - Chorioamnionitis, and
 - Maternal fever or infection.

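### SAP 12.5 takes hospitalizations out of the medically-attended events that protocol 8.4 counts, so the MAE tables could disagree with the investigators' flag

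*SAP*

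**What the plan says.** Protocol 8.4 defines an MAE by whether the event led to unplanned contact with a care provider. Its examples run from office visits to "home consultations, emergency room evaluations for non-life-threatening events, and hospitalizations". The Version 4.0 entry in protocol Appendix 5 shows that this was intended: "In addition to being serious adverse events, hospitalizations will now be categorized as medically-attended events". Section 8.4 also provides the data-entry field in which the investigator marks an AE as an MAE, as a significant new medical condition, or as both.

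SAP 12.5 opens with the same general rule but gives a shorter list. Emergency-room visits count only as "emergency room evaluations for non-life-threatening events that do not result in hospitalization", and a parenthesis adds that "life-threatening events or hospitalizations are SAEs, see Section 8.5 of the Protocol". The same section sets up the tabulation: "MAEs and SNMCs will be recorded and summarized from Day 0 to Delivery + 180 days for the maternal subjects", with infants covered from delivery to 180 days and later to 364 days.

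SAP 12.4, on infant AEs, takes a different route. It refers to any other SAE "or MAE or SNMC (as defined in Section 8.4 of the Protocol", which is the definition that includes hospitalizations.

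SAP 4.3.2 names MAEs as a maternal safety endpoint alongside SAEs, in the list "unscheduled medically-attended adverse events (MAEs), significant new medical conditions (SNMCs), and serious adverse events (SAEs". SAP section 17, on departures from the protocol, only refers back to protocol Version 10.0. None of the change lists in SAP section 18 mentions the MAE definition.

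**The concern.** The data are collected under one definition and may be tabulated under another. A site following the protocol flags a hospitalized event as an MAE. A programmer following SAP 12.5 literally would treat the same event as an SAE and leave it out of the MAE table. The table would then differ from the flag in the database and from the endpoint as the protocol defines it.

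The interpretive risk arises if the MAE table is read alone. If more cases of a diagnosis were admitted in one arm and fewer were handled in clinic, that arm would show fewer MAEs for the diagnosis, although medical attention had not fallen.

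**Working it through.** No formula applies, because the point concerns a definition. The check sets the rules side by side and follows a flagged event through to the tables.

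**Step 1. How each rule classes an event.**

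| Event | Protocol 8.4 | SAP 12.5 | SAP 12.4 (infants, via protocol 8.4) |
|---|---|---|---|
| Office, clinic or home visit | MAE | MAE | MAE |
| Non-life-threatening emergency-room visit, not admitted | MAE | MAE | MAE |
| Emergency-room visit followed by admission | MAE, and also SAE | Outside the list; assigned to SAE | MAE |
| Direct admission | MAE, and also SAE | Outside the list; assigned to SAE | MAE |

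The rules part on the last two rows. The protocol's emergency-room item is also confined to non-life-threatening events. The contradiction therefore turns on hospitalization, and a life-threatening event that is admitted falls under it.

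**Step 2. Which definition is intended.** The current text of protocol 8.4 carries the Version 4.0 change. The neighbouring entry in the Version 4.0 log separated intrauterine growth restriction from small for gestational age, and protocol Table 5 lists the two apart. SAP Table 2 still treats them as one entity. Two adjacent Version 4.0 changes are thus absent from adjacent SAP sections. This suggests old text carried forward, which is an inference: neither document says so.

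**Step 3. What reaches the MAE table.** The investigator sets the flag under protocol 8.4. If SAP 12.5 is used as a filter, flagged events with an admission are dropped. If the table simply counts the flag, they stay. The SAP states no derivation step that removes them, so the omission depends on how 12.5 is implemented.

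**Step 4. Where the events still appear.** In-patient hospitalization is an SAE criterion in SAP 12.7, which provides the SAE listing. SAP 12.2 tabulates unsolicited AEs, including SAEs for mothers and by seriousness for infants. SAP 12.4 summarizes infant SAEs by system organ class and preferred term. A hospitalized event left out of the MAE table is still reported in these outputs.

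**Step 5. Size.** A subject leaves the overall MAE numerator only if every MAE flagged for that subject involved an admission. The only overall MAE rates in the documents are for infants in the earlier pregnancy study (protocol 1.6.2): 89% placebo and 82% active, from 28 and 22 mothers. With most infants having at least one MAE, few would be expected to have only hospitalized ones. That rests on the assumption that most admitted infants also had an outpatient contact flagged as an MAE. No overall maternal MAE rate is given, and neither document gives the hospitalized share for any preferred term, so no effect by term can be computed.

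**The case against.** The strongest reply is that the tables may come out right anyway. The flag is the investigator's, set under the protocol. SAP section 3 says that the analyses accord with the protocol, SAP 12.4 cites protocol 8.4, and no step strips hospitalized events from flagged MAEs. This stands, and it makes the consequence conditional.

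A second reply is textual. The list in SAP 12.5 is illustrative, the limiting phrase attaches to emergency-room visits, and the parenthesis does not expressly say that an SAE cannot also be an MAE. An event with a clinic visit before admission still meets the general rule. This is arguable but weak. The parenthesis explains why hospitalizations are missing from the list, and exclusion is its natural reading.

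A third reply is that no safety information is lost and no success criterion depends on MAE counts, since the safety objectives are descriptive. This stands in full. A shift from clinic to hospital would show as a rise in SAEs.

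A reader might infer that for diagnoses such as bronchiolitis or sepsis most of the MAE row would vanish. The documents do not support this, as they give no hospitalized share for either term. Bronchiolitis is also a poor illustration of a clinic-to-admission shift. Under protocol 6.2.5, respiratory events captured as efficacy endpoints enter the AE record only if they are SAEs, so outpatient cases captured that way would not be in the AE tables to begin with.

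**Conclusion.** The inconsistency is real and stands in current text: SAP 12.5 contradicts protocol 8.4, and SAP 12.4 sides with the protocol. If 12.5 is applied as written, the MAE summaries could omit hospitalized events that investigators flagged. The MAE percentages would then match neither the flag nor the protocol's definition of the endpoint. This is a wrong rule in the SAP and not merely a missing detail, but its consequence is minor.

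Two stronger readings are tempting. One is that the MAE endpoint will certainly omit its most serious events; the SAP contains no instruction that makes this certain, and those events remain in the SAE and overall AE outputs. The other is that the sponsor chose a narrower MAE analysis; no departure is declared anywhere, and the surrounding text looks more like an amendment not carried over.

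That the overall MAE percentage would change little is a judgement. It rests on infant rates from one small earlier study and on the assumption in Step 5, and it has no overall maternal figure behind it.

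**What to change.** Replace the MAE definition in SAP 12.5 with that of protocol 8.4. State that the MAE summaries tabulate every AE flagged as an MAE, hospitalizations included, and that an event flagged both MAE and SAE appears in both tables. If the narrower definition is in fact wanted, declare it in SAP section 17 as a departure from the protocol and reconcile SAP 12.4 with it.

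The cost is SAP wording, with no new data. The small downside is that some events appear in both the MAE and the SAE table, which the protocol intends; a table footnote can say so. The change is best made before treatment codes are released for the Day 180 analysis, so that the definition is not settled with the allocation known. If that point has passed, describe the choice in the study report, as SAP 14.1 requires for departures from plan.

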12.6. Maternal/Fetal/Neonatal Adverse Events of Special Interest

Table 2 summarizes and defines a series of maternal/fetal/neonatal adverse events that are of special interest in the evaluation of maternal immunization strategies. The majority of these events will fulfill one or more of the criteria listed below (Section 12.7) for SAEs. In the event that one of these events does not meet the criteria for an SAE (e.g., "Small for Gestational Age" might not), it will nonetheless be reported as an SAE using the same reporting requirements as an SAE. The majority of these terms and definitions are derived from the Brighton Collaboration Definitions of Key Terms (WHO meeting July 2014). Some maternal/fetal/neonatal AESIs are open to interpretation as to which subject should be recorded as sustaining the event. **Table 2** also designates to which subject each class of event should be assigned; solely as a uniform data collection convention. Since there are multiple potential sources to determine the gestational age (GA) at birth, the study defined EDD and the birth date will be used to determine the GA at birth for the summary of the preterm birth categories (Very preterm and Moderate to late preterm).

Table 2: Maternal/Fetal/Neonatal Adverse Events of Special Interest

Term	Definition	Reported as an Event In
Stillbirth:	Delivery of a dead fetus of > 22 weeks gestation, subcategorized as: 
• Antepartum• Intrapartum	Mother
Placental Abruption:	Placental separation from the uterus with bleeding (concealed or vaginal) before fetal birth, with or without maternal/fetal compromise	Mother
Preterm Birth:	Delivery of a live newborn child, subcategorized as: 
• Very preterm: 28 to < 32 weeks gestation• Moderate to late preterm: 32 to < 37 weeks gestation	Mother
Gestational Hypertension/Pre-Eclampsia/Eclampsia:	Gestational Hypertension: New onset elevations of blood pressure after 20 weeks of gestation, in the absence of accompanying proteinuria. Pre-Eclampsia: A hypertensive disorder of pregnancy with: 
• A blood pressure $\geq 140/\geq 90$ on 2 occasions, at least 4 hours apart after 20 weeks of gestation, or a blood pressure $\geq 160/\geq 110$ and the presence of	Mother

Table 2: Maternal/Fetal/Neonatal Adverse Events of Special Interest

Term	Definition	Reported as an Event In
	
proteinuria (≥ 300 mg of urinary protein / 24 hours; or protein/ creatinine ratio ≥ 0.3, dipstick reading of 1+), or
 
 • In the absence of proteinuria, new-onset hypertension with the new onset of any of the following: 
 ○ Thrombocytopenia (platelet count $< 100,000/\mu\text{L}$), ○ Renal Insufficiency (serum creatinine concentrations $> 1.1 \text{ mg/dL}$ or a doubling of the serum creatinine concentration in the absence of other renal disease, ○ Impaired liver function, ○ Pulmonary edema, ○ Cerebral or visual symptoms. 
Eclampsia: All components of Pre-Eclampsia, with convulsions.
	
Third Trimester Hemorrhage:	Any third trimester bleeding with the etiology specified and may include, but not limited to, placenta previa, vasa previa, placental abruption.	Mother
Neonatal Death*:	Death of a live newborn child at any time from birth to 28 days of life, regardless of gestational age based on the following subgroups: 
 • Very early neonatal death: < 24 hours • Early neonatal death: birth to < 7 days • Late neonatal death: 7 to < 28 days 	Infant
Infant Death*:	A post-neonatal death that occurs between 28 days and 1 year of life.	Infant
Low Birth Weight:	Subcategorized as: 
 • Low birth weight: $< 2,500$ grams • Very low birth weight: $< 1,500$ grams • Extremely low birth weight: $< 1,000$ grams 	Infant
Small for Gestational Age (SGA):	Also referred to as intrauterine growth restriction or retardation (IUGR), is defined as a birth weight $< 10\%$ for infants of the same gestational age and gender, in same population.	Infant
Asphyxia:	Insufficient oxygen supply to organs at birth resulting from inadequate ventilation or perfusion.	Infant
Neonatal Encephalopathy:	A disturbance of neurological function manifested by difficulty initiating and maintaining respiration, depression of tone and reflexes, abnormal level of consciousness and often seizures. Categories of neonatal encephalopathy include: 
 • Due to hypoxic insult (intrapartum), • Due to another cause. 	Infant
Hypoxic-Ischemic Encephalopathy:	A syndrome of abnormal neurological behavior in the neonate, which is frequently associated with multi-system	Infant

Table 2: Maternal/Fetal/Neonatal Adverse Events of Special Interest

Term	Definition	Reported as an Event In
	dysfunction and follows severe injury before or during delivery associated with hypoxic and/or ischemic event.	
Sudden Infant Death Syndrome (SIDS):	Sudden death of any child under 12 months of age which remains unexplained after excluding other causes of death.	Infant

*Neonatal and infant deaths should be reported whenever possible as the *underlying medical condition which results in death*, with death captured as the outcome of the SAE. This allows the capture of more granular information about the incidence of specific diagnostic entities leading to death, and prevents confusion with SIDS in analysis.

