8.6 Maternal/Fetal/Neonatal Adverse Events of Special Interest

[Table 5](#) summarizes and defines a series of maternal, fetal, and neonatal adverse events that are of special interest in the evaluation of maternal immunization strategies. The majority of these events will fulfill one or more of the criteria listed above for SAEs. In the event that one of these events does not meet the criteria for an SAE (e.g., “Small for Gestational Age” might not), it will nonetheless be reported as an SAE using the same reporting requirements as an SAE. The majority of these terms and definitions are derived from the Brighton Collaboration Definitions of Key Terms (WHO meeting July 2014). Investigators should strive to collect the same level of data as for any SAE, and are encouraged to use the exact terms in [Table 5](#) to report events meeting these definitions (see [Table 5](#) footer for exceptions for reporting of neonatal and infant death). Note that the SAE eCRF/eSource will provide a field for designating an SAE report as a Maternal/Fetal/Neonatal Adverse Event of Special Interest (MFNAESI). Some MFNAESIs are open to interpretation as to which subject should be recorded as sustaining the event. [Table 5](#) also designates to which subject each class of event should be assigned; solely as a uniform data collection convention. Since there are multiple potential sources to determine the GA at birth, the study defined EDD and the birth date will be used to determine the

gestational age (GA) at birth for the summary of the preterm birth categories (Very preterm and Moderate to late preterm).

Table 5: Maternal/Fetal/Neonatal Adverse Events of Special Interest

Term	Definition	Reported as an Event In
Stillbirth:	Delivery of a dead fetus of > 22 weeks gestation, subcategorized as: 
 • Antepartum • Intrapartum 	Mother
Placental Abruption:	Placental separation from the uterus with bleeding (concealed or vaginal) before fetal birth, with or without maternal/fetal compromise	Mother
Preterm Birth:	Delivery of a live newborn child, subcategorized as: 
 • Very preterm: 28 to < 32 weeks gestation • Moderate to late preterm: 32 to < 37 weeks gestation 	Mother

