Gestational Hypertension/ Pre-Eclampsia/ Eclampsia:	Gestational Hypertension: New onset elevations of blood pressure after 20 weeks of gestation, in the absence of accompanying proteinuria. Pre-Eclampsia: A hypertensive disorder of pregnancy with: 
 • A blood pressure $\geq 140/\geq 90$ on 2 occasions, at least 4 hours apart after 20 weeks of gestation, or a blood pressure $\geq 160/\geq 110$ and the presence of proteinuria (≥ 300 mg of urinary protein / 24 hours; or protein/ creatinine ratio ≥ 0.3, dipstick reading of 1+), or • In the absence of proteinuria, new-onset hypertension with the new onset of any of the following: 
 ○ Thrombocytopenia (platelet count $<100,000/\mu\text{L}$), ○ Renal Insufficiency (serum creatinine concentrations > 1.1 mg/dL or a doubling of the serum creatinine concentration in the absence of other renal disease), ○ Impaired liver function, ○ Pulmonary edema, ○ Cerebral or visual symptoms. Eclampsia: All components of Pre-Eclampsia, with convulsions.	Mother
Third Trimester Hemorrhage:	Any third trimester bleeding with the etiology specified and may include, but not limited to, placenta previa, vasa previa, placental abruption.	Mother
Neonatal Death*:	Death of a live newborn child at any time from birth to 28 days of life, regardless of gestational age based on the following subgroups: 
 • Very early neonatal death: < 24 hours • Early neonatal death: birth to < 7 days • Late neonatal death: 7 to < 28 days 	Infant

Table 5: Maternal/Fetal/Neonatal Adverse Events of Special Interest

Term	Definition	Reported as an Event In
Infant Death*:	A post-neonatal death that occurs between 28 days and 1 year of life.	Infant
Low Birth Weight:	Subcategorized as: 
 • Low birth weight: < 2,500 grams • Very low birth weight: < 1,500 grams • Extremely low birth weight: < 1,000 grams 	Infant
Intrauterine Growth Restriction or Retardation (IUGR):	A fetus whose estimated weight is below the 10 th percentile for gestational age and whose abdominal circumference is below the 2.5 percentile.	Infant
Small for Gestational Age (SGA):	Defined as a birth weight < 10% for infants of the same gestational age and gender, in the same population.	Infant
Asphyxia:	Insufficient oxygen supply to organs at birth resulting from inadequate ventilation or perfusion.	Infant

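### SAP Table 2 treats IUGR as another name for SGA, whereas protocol Table 5 defines them as two separate infant events of special interest

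*SAP*

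**What the plan says.** Protocol Section 8.6, Table 5, lists the maternal, fetal and neonatal events of special interest and names the subject in whom each is recorded. IUGR and SGA have adjacent rows, both assigned to the infant. The IUGR row concerns the fetus: an estimated weight under the 10th percentile for gestational age, in a fetus "whose abdominal circumference is below the 2.5 percentile". The SGA row concerns the newborn: a birth weight below 10% "for infants of the same gestational age and gender, in the same population". The SGA row does not mention IUGR.

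SAP Section 12.6, Table 2, carries this list into the analysis plan without an IUGR row. Its SGA row reads "Also referred to as intrauterine growth restriction or retardation (IUGR" and then defines the event by birth weight, with the same cut-off as the protocol's SGA row. Neither fetal measure appears.

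On reporting, protocol Section 8.6 encourages sites to use the Table 5 terms as written, and says that the SAE form "will provide a field for designating an SAE report as a Maternal/Fetal/Neonatal Adverse Event of Special Interest (MFNAESI". SAP Section 12.6 adds that where such an event falls short of the SAE criteria, "it will nonetheless be reported as an SAE using the same reporting requirements as an SAE".

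**The concern.** Both texts are current, and they cannot both be right about what IUGR is. The SAP states that it implements protocol version 10.0, and version 10.1 restores a phrase in the title and is otherwise identical. The analysis table should therefore carry the protocol's definitions. Instead, a fetal finding with two conditions is described as a synonym for a birth-weight finding with one.

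The term deserves care in a trial of a vaccine given in the third trimester. Exclusion criterion 2 (protocol Section 5.2) keeps out women with evidence of growth restriction in the current pregnancy, so an IUGR report made later should mostly be a new finding after enrolment. A safety reader would want to see such reports under their own definition, apart from newborns who are simply light for their gestational age.

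**Working it through.** The plan gives no figure to reproduce and no arithmetic applies. The check is a comparison of texts.

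**Step 1: the rows.** Protocol Table 5 has 5 terms recorded in the mother and 9 in the infant, 5 + 9 = 14. SAP Table 2 has the same 5 maternal terms and 8 infant terms, 5 + 8 = 13. The missing row is IUGR.

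**Step 2: whether the definitions are interchangeable.** Cross the protocol's fetal criterion with the birth-weight criterion:

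| Meets fetal IUGR criteria | Birth weight under SGA cut-off | Protocol Table 5 | SAP Table 2 |
|---|---|---|---|
| Yes | Yes | IUGR and SGA | one combined event |
| Yes | No | IUGR only | not an event by definition; if reported as IUGR, filed as SGA |
| No | Yes | SGA only | SGA, also labelled IUGR |
| No | No | neither | neither |

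The tables give the same classification only in the last row. In the second row an infant who meets the protocol's definition is missed or misfiled. In the third row an infant without the fetal finding takes the IUGR label. In the first row the two events can no longer be told apart.

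**Step 3: whether the SAP explains the merger.** Section 17, on changes from the protocol's analyses, only refers the reader to the protocol. The version lists in Section 18 do not mention it. As background only, the protocol's history for version 4.0 (Appendix 5) records that IUGR "will now be captured as a separate entity, distinct from" SGA, so the split was deliberate. The finding does not rest on that log, because current Table 5 carries the split itself.

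**Step 4: where a reported IUGR event goes.** SAP Section 12.4 codes every infant adverse event by MedDRA system organ class and preferred term. Sections 12.1 and 12.4 summarize these events by class, term and treatment group. Section 12.2 adds a residual by-group tabulation of infant events that it does not name individually, and IUGR and SGA both fall there. A reported case therefore reaches a by-arm table under its preferred term. The documents do not say what that term is, or whether SGA shares it. A preferred-term count is also not a count of events meeting the Table 5 criteria.

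**The case against.** A reader might infer from the missing row that IUGR would not be tabulated by arm at all. The documents do not support that. Collection follows the protocol's terms, these events are handled as SAEs, and coded infant events are summarized by treatment group.

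A reader might also infer that the SAP plans an output that pools the two events. It does not say so. Section 12.6 defines terms, and the only summary it mentions is of the preterm birth categories. The lack of an explicit by-arm table affects most Table 2 terms and is not particular to IUGR.

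Nor is a listed endpoint dropped. IUGR is not named among the safety endpoints (protocol Sections 3.2.4.1 and 3.2.4.2; SAP Sections 4.3.1 and 4.3.2) or in the safety analyses of protocol Section 10.6. It is a pre-specified reporting term.

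Finally, the documents give no rates for IUGR or SGA, so nothing in them supports a claim that pooling would hide an imbalance of a particular size. Protocol Appendix 1 schedules ultrasound only at screening, so the fetal criteria would be met after vaccination mainly through imaging outside the protocol, and reports may be few. Safety is summarized as percentages with 95% confidence intervals, and chi-square tests are optional (SAP Sections 12.1 and 12.2), so no decision rule depends on this category.

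All of that stands, and it limits the consequence. It does not remove the contradiction: the SAP states a definition of IUGR that the protocol does not use, and does not say why.

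**Conclusion.** The contradiction between the two current tables is confirmed, and the SAP definition is wrong against the protocol. The consequence is limited to IUGR losing its place as a distinct special-interest category. The harm is conditional: it arises if a special-interest grouping or summary is programmed from Table 2.

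Two things remain unknown. One is the preferred term to which IUGR is coded, which decides whether the MedDRA tables separate it from SGA. The other is how consistently sites use the exact Table 5 term: the form's flag marks a report as a special-interest event, but the documents do not say that it records which one.

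No numerical size can be given. The point is minor: a safety definition to be aligned, with no bearing on efficacy, Type I error, power or sample size.

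**What to change.** In SAP Table 2:

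- Delete the clause beginning "Also referred to as intrauterine growth restriction or retardation (IUGR" from the SGA row, leaving the birth-weight definition.
- Add the protocol's IUGR row, with both fetal criteria and assignment to the infant.

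In the text of Section 12.6, state that IUGR and SGA will be tabulated separately by treatment group in Safety-I, with an infant who meets both counted once in each row. Record the change in Section 18. It would be sensible to make the same statement for the other Table 2 terms.

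The cost is SAP wording and a table shell. No new data collection is needed, provided that sites reported IUGR under its own term as the protocol encourages.
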